Enhancing Locomotor Learning with Motor Imagery and Transcranial Direct Current Stimulation: A Pilot Randomized Controlled Trial in Young Adults.

NCT06414213

09-20-2022

Study protocol

Study Design

The primary goal of this study is to investigate an novel intervention on improvements in walking and balance. The design of this study is a randomized, double-blinded clinical trial. The study will use a pilot intervention that will utilize a dual strategy combining MI with tDCS (a non-invasive brain stimulation) to activate the frontal/executive networks of the brain to enhance motor learning to increase retention and transfer of locomotor learning. Participants, separated by age by age 18-35 and 50 and older, will be randomly allocated to experimental (active tDCS) or sham groups and will be assessed at baseline, immediately following the intervention, and at 1-week. Outcome measures include cortical activation (oxygenated Hemoglobin, HbO₂), assessed through functional near-infrared spectroscopy (fNIRS), cognitive assessments, and gait and balance assessments. Complete participation will consist of 2 visits to the Neuromechanics laboratory at Leon Levine Hall.

Outcome Measures

Assessments will be conducted by the experienced examiner(s) blinded to group tDCS assignment and will occur at three time points: baseline, post-Intervention, and follow-up (1 week after the baseline assessment). Prefrontal cortical activity will be assessed during walking to investigate intervention-induced prefrontal/executive activity changes. Using a commercially available Functional near infrared spectroscopy (fNIRS) monitor (OctaMon by Artinis Medical Systems), changes in oxygenated hemoglobin concentration (O₂Hb) relative to a baseline task will be measured for the orbitofrontal and dorsolateral prefrontal cortex. During walking assessments, we will use fNIRS to measure frontal cortical activity. Changes in O₂Hb will be assessed at baseline and after the intervention week. All manufacturer guidelines will be followed in the collection of fNIRS.

Time to completion: Participants will walk over a 4-m instrumented walkway mat during the assessments. The walkway system is a clinical instrument that allows for objective gait assessment. Spatial and temporal gait variables calculated from the walkway system have strong concurrent validity and test-retest reliability (intra-class coefficients >0.8 for most variables). These measures will allow us to determine time to completion and changes in gait quality (stepping characteristics) during pre/post/ and follow-up testing.

Kinesthetic and Visual Imagery Questionnaire (KVIQ): The ability to imagine movements was assessed with the KVIQ. This test evaluates the subject's ability to see (visual imagery) and feel (kinesthetic imagery) movements. The KVIQ consists of 10 items, (5 movements for each scale), each item being a separate movement followed by rating the ease or difficulty of generating those self-images on a 5-point Likert scale (where 1 = no image or sensation and 5 = Image as clear as seeing or as intense as executing the action). Higher scores reflected higher imagery abilities.

Baseline visit and Intervention

We will enroll 40 adults age 18 to 35 (n=20) and 50 and older (n=20) without neurological conditions. Participants will be randomized to one of the two groups: 1) MI with sham tDCS ('MI /sham') and 2) MI with active tDCS ('MI/ active').

For Visit One, All participants will undergo fNIRS, Gait assessment, and KVIQ. Additionally, all participants will perform the locomotor learning task.

Locomotor Learning

Participants will begin in a quiet, standing position with the fNIRS attached to themselves and after a period of 30 secs of quiet rest, participants will stand for a period of 30 secs and then begin walking over the course. The course is a 10-meter obstacle course containing foam obstacles of various heights and widths at their fastest safe pace. Participants will repeat this process 10 times. Participants will be asked not to speak and only engage in thinking about the walking course. Rest periods of a minimum of 1 min will be permitted to prevent fatigue and standardize the procedures. Time to complete the course will be recorded and the change in time to complete the course will be used as an outcome.

Following the baseline testing and locomotor learning assessment, the participants will engage MI with active or sham tDCS intervention. Participants enrolled will receive standardized instructions explaining the protocol and undergo the assessment using a 24-in computer to watch video clips. Instructions, "Please watch the following video. You will see someone walking over the course you did for the baseline visit, which will be repeated several times. Place your focus on each foot as it approaches each obstacle and imagine performing the task yourself during the entire period of the video. At the end of the video you will be asked to close your eyes and to continue performing

mentally the task until you hear the stop sign. From time to time, I will encourage you to perform the task. Now try to relax and press the spacebar to start the video while concentrating as much as possible on the task when you are ready." This will be implemented to cue participants' visual attention to the obstacles and anatomical regions that are fundamental for correctly and safely walking the course, as consistently emphasized by physical therapists and gait rehabilitation experts. This method has been utilized in previous investigations and used during the intervention, The anodal electrode will be placed over the frontal cortex (F3/4 10:20 location) contralateral to the test side, and the cathode will be placed over the supraorbital region ipsilateral to the test leg (opposite side as the anode). Prior to placement of the electrodes, the area will be inspected for signs of scalp irritation and the scalp will be cleared with an alcohol pad. Electrodes will be secured with an elastic strap around the forehead and top of head (EasyStrap, Soterix). A Soterix clinical transcranial electrical stimulator will be placed within a clear backpack to be worn by the subject. The investigator will explain the stimulus to the patient (a tingling or itching sensation) and provide a pre-stimulus tickle to ensure proper electrode impedance (measured by stimulator) and familiarize the subject. The investigator will enter a specific subject code that will initiate either a sham current (2-minutes ramp on followed by no stimulation), or a constant 2.0mA current for the sham or tDCS groups, respectively. The current (or sham current) will go on for 18-minutes as participants perform a movement intervention. tDCS will be performed using a Soterix Clinical Trial stimulator and Soterix sponges. All manufacturer guidelines will be followed in its usage.

The groups will watch a standardized video sequence consisting of five walking trials (5 video clips—each trial representing 1 clip) over the 10m complex walking course containing the intermittent soft surfaces (foam mats). Participants will watch the video first at normal play speed and then in slow motion after a short break (30 secs to 1 min). Total training time will be approximately 20 mins, consistent with the locomotor intervention's duration and stimulation. Literature dictates that 15 to 30 mins of observation

is an appropriate duration for observational learning protocols to observe improvements. The model video sequence will show a typical pass through the complex walking course by a gender matched model.

Follow up

All participants will then return after one week and repeat the baseline assessments. Including the fNIRS, Gait assessment, and KVIQ and the locomotor learning task.

Statistical Design

Times of the three trials at each test will be averaged to observe any learning effects during the obstacle course. $\Delta\text{O}_2\text{Hb}$ at each of the 3 trials during each test were averaged. A 2-way factorial ANOVA with a between-subjects factor of group (3 levels) and a within-subjects factor of time (3 levels) will be used. In the case of significant interactions of main effects, pairwise comparisons using Fisher's LSD will be used post-hoc. Effect sizes will be interpreted from partial eta squared as small=0.01, medium=0.06, and large=0.14. Independent samples t-tests will be used to analyze any differences in the MIQ-3, and the tDCS sensitivity between groups.

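### The group-by-time ANOVA gives three groups for two arms, and its interaction cannot by itself show retention; the 1-week arm contrast and the LSD rule need to be named.

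*Combined protocol and SAP*

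**What the plan says.** The combined protocol and SAP sets out the comparison in a few places.

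- **Statistical Design:** "A 2-way factorial ANOVA with a between-subjects factor of group (3 levels) and a within-subjects factor of time (3 levels) will be used". The follow-up rule begins "In the case of significant interactions of main effects, pairwise comparisons using" and names Fisher's LSD. It lists no pairs, no covariate and no primary time point.
- **Baseline visit and Intervention:** "Participants will be randomized to one of the two groups", namely motor imagery with sham or with active tDCS. Enrolment is 40 adults, 20 in each age band.
- **Study Design:** participants "will be assessed at baseline, immediately following the intervention, and at 1-week", so baseline is one of the three time levels. The intervention is meant "to enhance motor learning to increase retention and transfer of locomotor learning". On allocation: "Participants, separated by age by age 18-35 and 50 and older, will be randomly allocated to experimental (active tDCS) or sham groups".
- **Locomotor Learning:** a change in course completion time is named as an outcome. The text does not say whether this is change across repeated walks or across visits, and Statistical Design ties no test to it.
- **Outcome Measures:** assessments are set at three times, but O2Hb change is then described at baseline and after the intervention week, which reads as two.

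**The concern.** The level count contradicts the design. Beyond that, the plan does not say which result would answer the retention question. Read with two arms, it offers three kinds of result:

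- **Group main effect.** It averages in the pre-treatment value, so it carries only two thirds of a lasting effect.
- **Group-by-time interaction.** It uses baseline and tests whether the arms change differently. It does not say when they differ.
- **LSD comparisons.** If these compare arms at 1 week, they ignore a baseline already collected. If they compare times within an arm, they are not a randomised comparison.

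The trigger for LSD is also ambiguous. A practice effect over time is to be expected on a repeated course. If a significant time effect is enough to open between-arm comparisons, they are in practice unprotected. At stake are a clear answer on retention, some power, and the false-positive rate of the follow-up.

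**Working it through.** **1. Level count.** Arms give 2 levels, age bands 2, and arm by age band 2 x 2 = 4. Nothing in the documents gives 3. With N = 40 the degrees of freedom are:

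- group: 1 and 38 with two levels (2 and 37 as written);
- interaction: 2 and 76 with two levels (4 and 74 as written).

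**2. Assumptions for the sizes below.** The documents give no SD, target effect, correlation, allocation ratio or power basis. I assume SD 1, a 0.5 SD effect, 20 per arm, two-sided 5%, compound symmetry with correlation rho, no age gap and no dropout.

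**3. Interaction.** The noncentrality is lambda = (n/2) x SS/(1 - rho), where SS is the squared deviation of the arm-effect profile from its own mean.

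- Lasting effect, profile (0, 0.5, 0.5): mean 0.333; SS = 0.1111 + 0.0278 + 0.0278 = 0.1667.
- Effect gone by 1 week, profile (0, 0.5, 0): mean 0.167; SS = 0.0278 + 0.1111 + 0.0278 = 0.1667.

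The two are identical. In both cases lambda = 10 x 0.1667/(1 - rho) = 3.33, 5.56, 8.33 and 16.67 at rho 0.5, 0.7, 0.8 and 0.9.

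**4. Power for a 1-week arm difference.** The standard error is sqrt(2V/20), with V = 1 unadjusted, 2(1 - rho) for the change score and 1 - rho^2 for ANCOVA. At rho 0.5, for example, ANCOVA has SE = sqrt(2 x 0.75/20) = 0.274, against 0.316 unadjusted. Power is from the noncentral t or F; the joint row is simulated. The ANCOVA row ignores chance baseline imbalance, and simulation puts it about one point lower.

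| Test, lasting effect | rho 0.5 | 0.7 | 0.8 | 0.9 |
|---|---|---|---|---|
| Interaction (same if the effect is gone by 1 week) | 34% | 53% | 72% | 96% |
| 1-week ANCOVA with baseline | 43% | 58% | 73% | 94% |
| 1-week arms, unadjusted | 34% | 34% | 34% | 34% |
| The same, also requiring a significant interaction | 15% | 21% | 27% | 33% |
| 1-week change score | 34% | 51% | 68% | 93% |

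The group main effect tests 0.5 x 2/3 = 0.333 with SD sqrt((1 + 2 rho)/3). Its power falls from 24% to 19% as rho rises from 0.5 to 0.9.

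**5. LSD trigger.** A 2 x 3 layout has 15 cell pairs: 3 between arms at one time, 6 within an arm, and 6 that mix both. I took the three between-arm pairs under no arm effect, with an assumed 0.8 SD practice effect and 20,000 simulated trials per setting. The chance of at least one false difference is:

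- any significant effect, including time, opens LSD: about 13%, 11%, 10% and 9% at rho 0.5, 0.7, 0.8 and 0.9;
- only the interaction opens LSD: about 1% to 2%.

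Three independent tests would give 1 - 0.95^3 = 14.3%, so the first reading is close to no protection.

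**6. Age band.** With an assumed constant 1 SD age gap, 1-week ANCOVA has 40%, 56%, 71% and 94% power with baseline only, and 42%, 57%, 71% and 94% with age added. Age adds 0 to 2 points.

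**The case against.** The interaction is the usual test in this design. It uses baseline, and a constant age gap does not weaken it. As an omnibus test it has 72% power against 73% for 1-week ANCOVA at rho 0.8, and 96% against 94% at 0.9. The only correlation guide in the plan, test-retest coefficients above 0.8 for most walkway variables, points to that range, although it does not cover course time or O2Hb. In a pilot, the choice of ANCOVA is partly one of efficiency. All of this stands.

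Several stronger readings are tempting, but the documents do not support them.

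- **A third arm was intended.** Every design passage describes two; a drafting slip is more likely.
- **The plan ignores baseline or its main test is invalid.** The interaction answers this.
- **Power for retention is less than half of what it could be.** That sets ANCOVA against an unadjusted comparison that must also follow a significant interaction, the least favourable reading. If the Locomotor Learning outcome means change from baseline to 1 week, ANCOVA gains only 9, 7, 5 and 1 points (43 - 34, 58 - 51, 73 - 68, 94 - 93).
- **Only power is at stake, not false positives.** This holds if the interaction alone opens LSD. It fails if a time effect can open it.
- **False positives are certainly inflated.** Many analysts would follow a time effect with time comparisons only; the text does not settle this.

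**Conclusion.** The level count is wrong as written. Independently of any power assumption, no arm contrast is named for retention, and the LSD pairs and trigger are not defined. That the interaction cannot separate a lasting from a vanished effect is algebra under compound symmetry.

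The size of the loss depends on the reading. For a lasting 0.5 SD effect with 20 per arm, ANCOVA gains 9 to 60 points over an unadjusted 1-week comparison (43 - 34 up to 94 - 34), but only about 1 to 9 over a 1-week change score. At rho 0.8 to 0.9 it gives no material gain over the interaction as an omnibus test. The false-positive chance is about 9% to 13% or 1% to 2%, depending on the trigger. These are illustrations on assumed values. The plan should be corrected, but its main model need not be discarded.

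**What to change.** 1. Correct group to two levels.
2. Name in advance one arm contrast for retention: the 1-week difference adjusted for the baseline value, by ANCOVA or a constrained-baseline mixed model, with age band as a second term. Test it whatever the interaction shows, and report it with a 95% CI. Under the assumptions above, the half-width is 2.028 x sqrt(2(1 - rho^2)/20), about 0.56 SD at rho 0.5 and 0.28 SD at rho 0.9.
3. Keep the interaction as a supporting test. Do not use the group main effect that averages in baseline as evidence of a treatment effect.
4. Let only a significant interaction open LSD comparisons between arms, and list the pairs.
5. Say what the change in course time in Locomotor Learning refers to and how it enters the model. Reconcile the O2Hb timing in Outcome Measures with the three time levels.

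The title reads "A Pilot Randomized Controlled Trial in Young Adults". If the age bands are analysed separately, the age term falls away but the baseline adjustment stands.

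The cost is SAP wording and one or two error degrees of freedom (38 to 37 or 36; at 36, critical t goes from 2.024 to 2.028). Baseline and age band are already collected. A 1-week contrast will not detect an effect that has gone by then, so the choice must be made before the data are seen.

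### The only planned ANOVA has no age-band term, although participants are enrolled and allocated by age band; if the bands are pooled, precision can be lost for nothing

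*Combined protocol and SAP*

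**What the plan says.** Study Design states that participants, "separated by age by age 18-35 and 50 and older, will be randomly allocated to experimental (active tDCS) or sham groups". This reads as allocation stratified by age, although no method is described. Under Baseline visit and Intervention the plan says "We will enroll 40 adults age 18 to 35 (n=20) and 50 and older (n=20) without neurological conditions" and then "Participants will be randomized to one of the two groups", namely motor imagery with sham or with active tDCS. Locomotor Learning adds that "the change in time to complete the course will be used as an outcome".

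Statistical Design gives one model for course time and O2Hb, a two-way ANOVA with a "between-subjects factor of group (3 levels) and a within-subjects factor of time (3 levels". It continues: "In the case of significant interactions of main effects, pairwise comparisons" by Fisher's LSD, with partial eta squared as the effect size. No age factor, age covariate, by-band analysis or pooling statement appears anywhere. The three levels of group cannot stand for age, because there are two arms, and two arms by two bands make four cells. The title describes the trial as "A Pilot Randomized Controlled Trial in Young Adults", while half the planned sample is 50 or older.

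**The concern.** Age band is known for every participant and is built into enrolment and, apparently, into allocation. If the bands are pooled in a model without age, differences between younger and older adults are counted as random error. There are two separate routes.

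- **Within-subject error.** If the bands differ in how much they learn, that difference enters the error of the group-by-time test, which is the test of the change in course time.
- **Between-subject error.** If one band is slower, or has a different O2Hb level, by a constant amount at every test, that gap enters the error of the group main effect, of a post-hoc arm comparison at one time point, and of the between-subject partial eta squared. It cancels from group-by-time and from change scores.

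With 40 people and no stated power, the trial has little precision to spare. Leaving open whether the bands are pooled or analysed separately also allows that choice to be made after the data are seen.

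**Working it through.** The plan gives no power or sample-size calculation, so there is no figure of its own to reproduce.

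**Inputs from the documents:** N = 40, two bands of 20, two arms, three assessments.

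**Assumed, because not stated:** 1:1 allocation balanced within band (20 per arm, 10 per arm per band); two-sided 5% level; no dropout; within-band SD 1 at each test; equal within-person correlation ρ of 0.6 or 0.7; true arm effect 0.6 SD at both later tests; level gap D and learning gap g between bands (g at both later tests), in SD units.

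**Group-by-time test.** For the pattern (0, g, g) over the three tests, the squared deviations from its mean sum to (2/3)g². The age-by-time sum of squares left in the error is therefore (40/4)(2/3)g² = 6.667g², on 76 error df with variance 1 − ρ:

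SE ratio = √[1 + 6.667g² / (76(1 − ρ))]

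- g = 0.5: √(1 + 1.667/30.4) = 1.027 at ρ = 0.6; √(1 + 1.667/22.8) = 1.036 at ρ = 0.7.
- g = 0.8: √(1 + 4.267/30.4) = 1.068; √(1 + 4.267/22.8) = 1.090.

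D does not appear in the formula, so a constant gap costs nothing here. The SD of the change score is √(2(1 − ρ)), which is 0.89 or 0.77. A learning gap of 0.8 is thus already 0.9-1.0 SD of change and is taken as the upper end.

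Simulated power of the 2-df F test (20,000 trials per setting), without age → with age and age-by-time:

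| Learning gap g | ρ = 0.6 | ρ = 0.7 |
|---|---|---|
| 0 (level gap 0, 1.0 or 1.5) | 57% either way | 69-70% either way |
| 0.3 | loss about 1 point | loss about 1 point |
| 0.5 | 54 → 57% | 67 → 70% |
| 0.8 | 49 → 56% | 62 → 70% |

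As a check on the full-model figures, the noncentrality is 6.667 × 0.6² / (1 − ρ) = 6.0 or 8.0. On 2 and 74 df that gives 57% and 70%. A separate simulation with other assumptions (effect 0.7, ρ = 0.7, learning gap 1 SD) gave 73-74% without age and 83-84% with it.

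**Arms at one time point.** The band sum of squares is (40/4)D² = 10D² on 38 df, so the SE ratio is √(1 + 10D²/38). For D = 1 this is √1.263 = 1.124. The 95% half-widths are:

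- without age: 2.024 × √(2/20) × 1.124 = 0.72 SD
- with age: 2.026 × √(2/20) = 0.64 SD

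Simulated power is 36-37% without age and 45-46% with it.

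**Group main effect.** The variance of a person's mean over three tests is (1 + 2ρ)/3 = 0.733 or 0.800. For D = 1 the SE ratio is √(1 + 0.263/0.733) = 1.17 or √(1 + 0.263/0.800) = 1.15.

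**Type I error without age, arms balanced within band.** Group-by-time is about 4.3% at g = 0.5 and 3% at g = 0.8. The group main effect is 2.2-2.5% at D = 1. The unadjusted tests are conservative.

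**Cost of the terms.** With two arms, error df go from 38 to 37 (between) and from 76 to 74 (within), and the critical F for group-by-time from 3.117 to 3.120. If age does not matter, simulated group-by-time power changes by 0.2 points or less.

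**If the bands are analysed separately.** With 10 per arm, the half-width is 2.101 × √(2/10) = 0.94 SD of the quantity analysed. The effect detectable with 80% power is 1.32 SD, against 0.91 SD with 20 per arm.

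**The case against.** The strongest reply is that the loss is small where the plan mainly looks. The outcome is a change in course time, tested through group-by-time. There a constant age gap costs nothing, and a moderate learning gap costs 1 to 3 points of power. The larger figures belong to the group main effect, which averages in the pre-intervention baseline, and to arm comparisons at one time point. The plan does not say that its post-hoc comparisons are of that kind; they may compare time points within an arm, where a constant gap cancels. All of this stands and limits the size of the point.

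It is also fair that conservatism depends on arms being balanced within band, which the plan does not guarantee. Under simple coin-flip allocation (6,000 trials per setting), group-by-time type I error without age was 4.8-5.3%. The gain from adding age was about nil at a 0.3 SD learning gap, 1.5-2.6 points at 0.5 SD and 5-9 points at 0.8 SD. So the gain at moderate gaps is smaller without stratification.

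Finally, if the bands are meant to be analysed separately, a model without age is correct within each band. The plan does not say so, and that choice would leave 10 per arm. The pilot label does not remove the point either: with 40 people, the width of the interval is much of what the trial has to report.

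**Conclusion.** The concern holds. The plan enrols and separates by age band, then specifies a single model that ignores it. If the bands are pooled, precision is lost when they differ in learning or when arms are compared at one level. On the assumptions above, group-by-time loses from nothing to 7-8 points of power, and a 1 SD level gap widens the post-test arm comparison by 12%. The true loss may be nil, since the documents give no age effect. The arm comparison is not biased. With arms balanced within band the tests err on the conservative side; under simple allocation they are close to nominal. The case for change rests on the imbalance of costs: a possible loss of several points of power against a few degrees of freedom.

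**What to change.** State in Statistical Design whether the age bands are pooled. If they are, replace the model sentence with wording such as:

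> Course time and O2Hb will be analysed with arm (active, sham) and age band (18-35, 50+) as between-subject factors and time as within-subject factor, including arm-by-time and age-by-time. The arm difference in change from baseline will be reported with a 95% CI overall and, descriptively, by age band.

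By-band results should stay descriptive, given their width at 10 per arm. State also how allocation is stratified by age. In the same edit, reconcile the three levels of group with the two arms, and the title's population with the one enrolled; these are separate inconsistencies that need no assumptions.

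The change is to text only. It needs no additional participants, visits or measurements.

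### As written, the group-by-time ANOVA drops anyone missing one of three occasions and assumes sphericity; the plan has no missing-data rule and no correction.

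*Combined protocol and SAP*

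**What the plan says.** The Statistical Design section plans a two-way ANOVA with three levels of group between subjects, and says that "a within-subjects factor of time (3 levels) will be used". Trials within a test are averaged, so each person contributes one value per occasion. Significant effects are followed by Fisher's LSD. The section does not mention a sphericity test or correction, a covariance structure, the error term for the LSD contrasts, missing data, or alpha.

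The timing comes from other sections. Study Design says "Complete participation will consist of 2 visits to the Neuromechanics laboratory", and Outcome Measures lists baseline, post-intervention and 1-week assessments. Baseline and post-intervention therefore share the first visit, separated mainly by the training ("Total training time will be approximately 20 mins"). Only the third occasion needs a return, which the Follow up section takes for granted: "All participants will then return after one week".

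On size and arms, the Baseline visit and Intervention section says "We will enroll 40 adults age 18 to 35 (n=20) and 50 and older (n=20) without neurological conditions" and "Participants will be randomized to one of the two groups". The allocation ratio is not given. The ANOVA's three group levels do not match the two randomized groups.

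**The concern.** A classical repeated-measures ANOVA needs all three values from each person. Someone who misses the return visit, or has one unusable recording, also loses the valid values from the other occasions. With 40 participants and no dropout allowance, that costs precision. It can also bias the comparison if return depends on how the post-test went.

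The uncorrected F test further assumes that all pairwise differences between occasions have the same variance. Two tests in one session will plausibly be more alike than either is to a test a week later. The interaction test, which carries the tDCS question, would then reject somewhat too often. Any pairwise contrast built on the pooled error term would have the wrong standard error, too large for the immediate effect and too small for the 1-week effect.

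**Working it through.** **Inputs.** From the documents: 40 participants, two arms, three occasions, two of them in one visit. Assumed, because the documents do not give them: 1:1 allocation (20 per arm), two-sided alpha of 0.05, equal SDs, and all correlations and dropout rates. The plan states no power or precision figure that could be reproduced.

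**1. Departure from sphericity.** Let r be the baseline-post correlation and s the correlation of each with week 1, with SD 1. The two orthonormal time contrasts are uncorrelated, with variances λ1 = 1 − r and λ2 = 1 + r/3 − 4s/3. Then epsilon = (λ1 + λ2)² / [2(λ1² + λ2²)].

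- r = 0.9, s = 0.6: λ = 0.1 and 0.5; epsilon = 0.36/0.52 = 0.69.
- r = 0.9, s = 0.7: λ = 0.1 and 0.367; epsilon = 0.2178/0.2889 = 0.75.
- Two correlations of 0.7 and one of 0.8: λ = 0.2 and 0.333; epsilon = 0.2844/0.3022 = 0.94.

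**2. Type I error of the interaction test.** Simulated with 40,000 trials per run and 20 per arm (Monte Carlo standard error about 0.1 point); ranges are over repeated runs.

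| Epsilon | Uncorrected | Greenhouse-Geisser |
|---|---|---|
| 0.69 | 6.6–6.9% | 4.7–5.0% |
| 0.75 | about 6.2–6.3% | 4.7–4.9% |
| 0.94 | about 5.0–5.4% | about 4.7% |

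**3. LSD contrasts, if the error term is pooled.** The variance of a difference between two occasions is 2(1 − correlation). The pooled term replaces all three variances by their mean. The critical t on 2 × 38 = 76 df is 1.992.

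- r = 0.9, s = 0.6: variances 0.2, 0.8, 0.8; mean 0.6. For baseline-post the effective critical value is 1.992 × √(0.6/0.2) = 3.45, so the null rejection rate is about 0.1%. For each week-1 contrast it is 1.992 × √(0.6/0.8) = 1.73, so the rate is about 9%.
- r = 0.9, s = 0.7: variances 0.2, 0.6, 0.6; mean 0.467. Critical values of 3.04 and 1.76 give about 0.3% and 8%.

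Simulation agrees with these approximations.

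**4. Listwise deletion.** If a fraction m misses week 1 equally in both arms, the standard error of the arm difference in baseline-to-post change is multiplied by 1/√(1 − m).

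- m = 10%: 36 of 40 remain; factor 1.05.
- m = 20%: 32 of 40 remain; factor 1.12.
- m = 30%: 28 of 40 remain; factor 1.20.

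Baseline and post values exist for everyone in each case.

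**5. Bias, as an illustration.** Suppose about 20% are missing at random and dropout depends on the post-test value in opposite directions by arm. With a true effect of −0.50 SD, completers gave −0.43 at 1 week and −0.57 immediately. The likelihood estimate at 1 week, and the immediate estimate from all participants, were both −0.50.

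**6. What an unstructured covariance costs (20 per arm, small-sample df).**

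- Sphericity true (all correlations 0.7), effect of 0.5 SD at post and week 1: power 51.3%, against 53.0% for the planned F.
- Epsilon 0.69, effect of 0.6 SD at week 1 only: 45.4%, against 56.6% for Greenhouse-Geisser.
- Epsilon 0.69, effect of 0.5 SD at post and week 1: 89.3%, against 45.4% for Greenhouse-Geisser.
- With a Wald chi-square in place of small-sample df, type I error is 6.6% to 6.9% at 20 per arm and up to 8.8% at 10 per arm.

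**The case against.** The strongest reply is that nothing in the documents fixes the size. With correlations of 0.7, 0.7 and 0.8 the inflation all but disappears. A Greenhouse-Geisser correction inside the planned ANOVA deals with the omnibus test. The trial is a small pilot in adults without neurological conditions, with one return visit, so dropout may be low. For O₂Hb, one sentence in Outcome Measures gives only two occasions, and with two levels sphericity does not arise. All of this stands and limits the point. It does not supply the missing rule or the missing correction.

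A reader might infer stronger claims that the documents do not support:

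- *A mixed model cures both problems at no cost.* It does not. Power moves in either direction (step 6), a random-intercept model would keep the equal-correlation assumption, and nothing here protects against data missing not at random.
- *Losing the slowest 10% of one arm at the post-test biases the result by 0.19 SD.* That is the shift in the raw post-test difference. The shifts are 0.14, 0.19 and 0.16 SD at the three occasions. The changes that the interaction tests therefore shift by only 0.19 − 0.14 = 0.05 and 0.16 − 0.14 = 0.02 SD.
- *Power falls from 73.5% to 68.7% with 10% dropout.* That is for an ANCOVA, which is not planned, with a 0.6-SD effect and a correlation of 0.7. At 0.9, the baseline-post correlation behind the type I figures above, it is 98.9% to 98.0%.

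**Conclusion.** The point holds as a moderate weakness of specification. Run as written, the ANOVA discards usable data from anyone with an incomplete record and relies on an assumption that the visit schedule makes doubtful.

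Under the assumed high within-visit correlation, the omnibus inflation is about one to two percentage points. The larger distortion is in the pairwise contrasts, but only if they use the pooled error term, which the plan leaves open. The precision loss follows directly from whatever share misses week 1. Whether this trial will in fact reject too often, or by how much, cannot be determined from the documents.

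**What to change.** Prespecify a likelihood-based mixed model on all available observations at the three occasions, with:

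- group (2 levels), time, group × time and age group as terms;
- unstructured covariance over time and Kenward-Roger degrees of freedom;
- missing at random stated as the assumption.

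Keep baseline as an outcome occasion, so that group × time still tests the tDCS effect. The alternative is to model the post-baseline values with baseline as a covariate. In that model group × time asks only whether the effect differs between post and week 1, so the group contrast at each time must be named as the test. Participants without a usable baseline would also still drop out.

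If the ANOVA is kept, report the Greenhouse-Geisser corrected F, use separate-error pairwise contrasts, and state how incomplete records are handled. In either case, correct the group factor to two levels and state whether O₂Hb has two or three occasions.

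The cost is SAP wording and standard software, with no new data. The statistical price of the mixed model is about 2 points of power if sphericity holds, and a gain or loss that depends on the effect pattern if it does not.
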